
Cost-effectiveness evaluation. We will assess both the clinical effectiveness in AKI reduction and the two interventions' cost-effectiveness. A cost effectiveness analysis will be conducted estimating the incremental cost for each incremental AKI prevented above the TA only baseline and stratified across the other three clusters. A

PROTOCOL

(Version #: 6, version date: 9-21-20)

separate budget impact analysis for implementing the VLC arm and stratified by ASR will be generated. Budget impact analyses estimate the cost to the hospital or service entity to implementing a new program or initiative.

C.8. Qualitative Methods. We will employ a qualitative approach in assessing site **fidelity** to the randomized intervention arm (TA, TA+ASR, VLC, VLC+ASR) and **implementation** of the interventions. Building off prior quantitative and qualitative work conducted by our research team, we will measure fidelity to the VLC, including participation on monthly calls, submission of key documents (i.e., homework), and a general active participation in the learning community in months 12 to 18 (see **Appendix 2**). We have mapped data collection tools including fidelity and implementation measures to the PARIHS framework constructs (see **Appendix 3**) to ensure we gather appropriate information for the context, facilitation, and evidence domains in PARIHS.⁵⁴ Semi-structured phone-based interviews with all team members together (without the catheterization laboratory director) at each site (TA and VLC) will occur at baseline, month 12 and 18 post-intervention to collect qualitative data on the participant experiences with the improvement process (**Appendix 3**). With these interviews, we hope to examine aspects of clinic culture that may support or hinder AKI prevention and the dynamics and organizational culture of the clinic. Such information (e.g., hierarchies and power dynamics, consensus and disagreement) will augment our understanding of barriers and facilitators of AKI prevention within real-world clinical settings.^{62,63} Interviews will be conducted at each site for each team member. These 1-hour interviews will be conducted using an interview guide to solicit in-depth information about the work of the staff, including the strategies to prevent AKI. Two qualitative researchers will lead the qualitative approach in assessing fidelity and implementation. Building on our prior work,³ interviews will ask about the fidelity of the appropriate strategies identified in our pilot work to improve AKI. We will also inquire about barriers and facilitators of implementing the identified strategies. Interviews, TA and VLC calls will be audio-recorded using a VA-approved audio recorder (VA Microsoft Teams Meeting) and transcribed by an approved federal contractor, Transperfect, and used for qualitative analysis (**C.8. Qualitative Analysis**).

Qualitative Analysis. Audio-recorded qualitative interviews will be transcribed, managed and analyzed with the aid of Atlas.ti, a qualitative analytic software program. We will conduct qualitative content analysis, a widely-recognized strategy for the interpretation of the content of text through systematic coding to identify patterns and themes.⁶⁴ We will approach our analysis through four coding levels: 1) descriptions of a priori themes based on the interview guide, 2) fidelity of the interventions, 3) unanticipated or emergent themes, and 4) barriers and facilitators to the implementation of strategies to improve AKI. Qualitative coding and content analysis will consist of identifying quotations that express a cogent theme or concept and labeling these quotations for categorization and summarization.⁶⁵ Coding is the pivotal link between data collection and deriving meaning from qualitative data.^{66,67} In the initial stages of coding, we will conduct 'open' coding, which is the process of labeling portions of text to identify and formulate all ideas, themes, and issues suggested by the data.^{66,68} Analytic

PROTOCOL

(Version #: 6, version date: 9-21-20)

codes constructed in the context of open coding are provisional and grounded strongly in the data.^{66,69} Through ongoing immersion in the dataset, we will proceed to ‘focused coding’, which utilizes the prominent themes identified during open coding as the basis for more fine-grained analyses.⁶⁹ We will compare different pieces of data for similarities and differences, known as a *constant comparisons* approach (comparing different pieces of data for similarities and differences). This will be done until no new categories or relevant themes emerge (point at which *thematic saturation* is reached).⁷⁰

Two analysts will code the qualitative data. Involving multiple analysts is a highly-regarded check on rigor in qualitative research as it allows for multiple perspectives and resolution of discrepancies through consensus.⁶⁹ We will review our coding approach and conduct regular consultations with the research team during the coding process. Based on previous qualitative studies, the selected sample size for the interviews is anticipated to achieve saturation of themes. Our analyses will yield an in-depth understanding of efforts and strategies to improve AKI at VA Medical Centers. We expect our findings will be generalizable to all VA and non-VA medical centers and generate hypotheses relevant to future efforts designed to improve AKI.

C.9. Scientific Rigor and Sex as a Biological Variable. We will enroll all eligible consecutive patients in our study including women. Our model includes the patient characteristics of sex and age. This will allow us to assess the beta coefficients of these biological variables and plot their marginal effects on AKI outcomes and their influence on our findings. While women are a smaller proportion of patients in the VA, sex will be incorporated (1 = woman, 0 = men) to determine mediating effects in women versus men and age will be modeled as a spline function to assess curvilinear effects dependent on patient age.

C.10. Rigor and Reproducibility. To ensure scientific rigor and reproducibility, an analytic program file used to produce the analyses and a de-identified dataset will be made available to third parties within the VA system to conduct confirmatory analyses for the proposed specific aims. All parties must be in compliance with VA regulations and access. All analytic results will be reported in supplementary appendices for all publications.

C.11. Sample Size and Power. To be conservative, power calculations assume the two-factor ANOVA with interaction. The target enrollment of approximately 2,644 is planned in each of the four arms of the study (TA, TA+ASR, VLC, VLC+ASR) with four hospitals within each arm (average approximately 661 patients per hospital). Based on national VA catheterization data for CKD patients,¹⁴ the proportion of AKI in the VLC and VLC+ASR arms are assumed to be 0.2700 under the null hypothesis and 0.2025 under the alternative hypothesis (an effect size of 25% or 0.0675). The proportion of AKI in TA and TA+ASR arms are projected at 0.2700 for the intervention period. We further assume an intra-cluster correlation coefficient (the ratio of variation between hospitals to the sum of variation within and between hospitals) of 0.0009 – this is implied by the intervention arm of the pilot study.³ We plan to conduct 0.05-level tests and desire

PROTOCOL

(Version #: 6, version date: 9-21-20)

power of at least 90%. The power for analysis to detect any difference at all across the four intervention studies can be approximated by assuming the distribution of the proportion of AKI cases under each strategy follows a normal distribution and applying an F-test with penalty for clustering. Under these assumptions, our power to detect any difference against the null of no difference is above 99%. We also compute power for illustrative individual contrasts of interest. The power to detect a significant effect of VLC within a level of ASR (i.e., either for ASR used or ASR not used) is also above 99% (although numerically lower than for the test of any difference across the four groups as sample size is halved) with a minimum detectable effect size of 0.034. If under the alternative hypothesis the proportion of AKI for the VLC arm was also 0.27 (so that an interaction effect is present), the power to detect a significant interaction between TA/VLC and ASR status is just above 90%. Power is lower for the interaction contrast due to four groups being compared as opposed to only two groups. In summary, we have overwhelming power to detect a difference among any of the four intervention strategies and between the levels of one factor within a level of the other factor, and acceptable power (i.e., above 90%) to detect a significant interaction between the effects of the factors. Finally, assuming a Bonferroni correction for multiple testing and a 25% effect size for each difference, testing the full set of 6 pairwise differences among the four intervention strategies has power >97% implying we will be adequately powered to infer the optimal intervention strategy.

C.12. Expected Outcomes. We expect to prevent AKI and improve outcomes in common diagnostic procedures. As depicted by the above power calculations, we expect to reject the null hypothesis that the interventions (TA, TA+ASR, VLC, VLC+ASR) will all produce the same reduced rate of AKI after the 18-month intervention period. Comparable to our pilot intervention, we expect the VLC with or without ASR to have more than a 25% reduction in AKI over the TA intervention with or without ASR, where we observed a 28% reduction among patients with pre-existing CKD,³ implying that the above power calculation likely errs on the side of being too conservative (i.e., we expect to have greater power). Using process measures from our fidelity tool and interviews, we expect to observe the VLC teams to successfully implement more AKI prevention strategies from our toolkit. At our 6-month semi-structured interviews of individual team members, we expect team members to report their teams achieving a hospital-wide shift in the attitudes and awareness of AKI prevention comparable to our pilot.³

C.13. Generalizability to non-VA sites. The VA offers a strong learning laboratory with existing standardization across sites. The VLC intervention was piloted in 10 non-VA hospitals. The ASR intervention, while developed in the VA for national ASR for AKI, can be ported to any EMR; daily data from the EMR laboratory or catheterization system would need to be directed to the mounted ASR toolkit in the data warehouse. Coding to allow the ease of portability to non-VA EMRs will be conducted by [name] during the award period. The AKI Prevention Toolkit and measures can be applied in any VA or non-VA site.

PROTOCOL

(Version #: 6, version date: 9-21-20)

C.14. Potential Problems and Alternative Strategies. One potential problem is **site enrollment**. Sample size estimates required a minimum of 16 sites (minimum of 4 in each arm); we have over-recruited 29 sites with planned over-enrollment in each arm to a minimum of 4 sites per arm; the two excess sites with the lowest volume will be excluded from the study. Another potential threat is **contamination** where providers from one condition educate providers in the comparison condition of their implementation group. Indeed, this is the reason why we have chosen to randomize at the site as opposed to the physician level, for which contamination would be highly plausible. In regards to our proposed site-level cluster design, we control for potential contamination by constraining team communications to the 4 sites in the same study condition. In addition, only the ASR sites will have website access to the ASR resources regulated by user login requirements. In addition, while login access is restricted to ASR, it is possible that ASR centers could directly share surveillance data with a non-ASR site, but beyond basic site risk-adjusted ranking, all other data will focus only on that site, which will limit possible contamination. First, we will evaluate the possibility of contamination through both quantitative measures of process improvements and qualitative data from calls and semi-structured interviews of team members. Second, we have systems in place to prevent transfer of recommendations on AKI Prevention Toolkit implementation from VLC sites or summary statistics on relative performance from the ASR sites to the TA site(s) or non-ASR site(s). Third, the TA sites will have the same number of calls, TA sites will not have access to the VLC structure, frequency, or level of team-based coaching. We have taken care in both the design and measurement to ensure contamination does not occur and if it does, it will inform our analysis.

Site level randomization may generate patient level imbalances between sites, and this requires that we adjust for patient-level characteristics in the statistical analyses as noted above (see Statistical Analysis).

Ascertainment of AKI is a potential issue for measurement bias. By focusing on patients with pre-existing CKD, we will limit the number of patients currently without measurement of serum creatinine up to 48- hours. Based on our extensive experience with the CART data and supplementary serum creatinine data from multiple sources within the VA, less than 5% of patients with pre-existing CKD do not have a post-procedure serum creatinine measured within 48-hours. Current VA standard of care is to have post-procedure serum creatinine measured for all CKD patients. We will strongly encourage sites to implement a routine clinical practice that is in compliance with the current guidelines as part of our educational quality improvement framework.

While setting up the study, we will be able to collect data from sites for a period of approximately 6-months before any interventions are unleashed. One strategy is to use these data to establish baseline covariates for each site, helping to account for unexplained variation between sites. However, with the ICC estimated to only be 0.0009, there is likely to be little utility in this. Another use is to allow the 4 intervention strategies to be compared to a pure control or baseline in which no intervention is used by pooling these data with the data.

PROTOCOL

(Version #: 6, version date: 9-21-20)

C.15. Specific Aim 2: Evaluate the sustained efficacy of the Virtual Learning Collaborative and/or Automated Surveillance Reporting to reduce the incidence of AKI following the intervention period.

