The proposed study asks whether supporting the use of the AKI Prevention Toolkit by 1) VLC coaching augmented by ASR (VLC+ASR) will lead to better patient outcomes compared to TA, TA + ASR, and VLC alone; and 2) VLC will be superior to TA with or without ASR. We will address these questions in a 2x2 factorial cluster-randomized trial that randomizes 16 hospitals to receive one of the following interventions for 18-months: A) Technical Assistance (TA); B) Technical Assistance with Automated Surveillance Reporting (TA+ASR); C) Virtual Learning Collaborative (VLC) with team-based coaching; and D) Virtual Learning Collaborative with Automated Surveillance Reporting (VLC+ASR). All sites have been recruited and will receive the AKI Prevention Toolkit (Appendix 1) that includes 3 core preventive interventions: 1. Standardized order sets; 2. IV and oral fluids; and 3. Reduced contrast volume. The interventions were developed and tested in our pilot to implement AKI preventive strategies.^{1,3}

PROTOCOL

(Version #: 6, version date: 9-21-20)

Specific Aims

Specific Aim 1: Compare the efficacy of a Virtual Learning Collaborative and/or Automated Surveillance Reporting compared to Technical Assistance to reduce the incidence of AKI.

Our working hypothesis is that multi-disciplinary clinical teams in a Virtual Learning Collaborative (VLC) with team-based coaching in process measurement and implementation methods will reduce the incidence of AKI following procedures, compared to a Technical Assistance (TA) intervention, both with or without Automated Surveillance Reporting (ASR). We also hypothesize that ASR will have a bigger impact with VLC than with TA.

Specific Aim 2: Evaluate the sustained efficacy of Virtual Learning Collaborative and/or Automated Surveillance Reporting to reduce the incidence of AKI following the intervention period.

Our working hypothesis is that VLC coaching augmented by ASR (VLC+ASR) will be superior to TA, TA +ASR, and VLC alone. Secondarily, VLC will be superior to TA with or without ASR. Sixteen hospitals will continue to enroll patients following the 18-month intervention period for an additional 18-months post-intervention with the TA, ASR, and VLC interventions removed. We will evaluate whether the reduced incidence of AKI will be sustained for each of the randomized clusters during the post-intervention phase.

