Impact: Evidence of the efficacy of Virtual Learning Collaborative, augmented by Automated Surveillance Reporting, on the sustained use of preventive interventions will enable hospitals to improve quality of care for the over 2 million patients undergoing cardiac catheterization and, as a result, reduce their significant risk of acute kidney injury. More broadly, these findings will be relevant to supporting hospital's implementation of a wide array of preventive interventions and has the potential for vastly improving patient care and outcomes.

Specific Aim 3: Laboratory Predictors of AKI in Patients Undergoing Coronary Angiography

In this aim, our goal is to examine whether lower serum magnesium, lower hemoglobin, higher hemoglobin A1c, and other laboratory predictors are associated with a higher risk of AKI in patients undergoing coronary angiography. We are defining AKI as a doubling of serum creatinine (SCr) or need for RRT. We will also examine whether laboratory predictors are associated with an increased risk of death at 30 days.

A. Background and Significance:

Over two million diagnostic or interventional cardiac catheterization procedures are performed in the United States each year.^{6,15} Acute kidney injury (AKI) is preventable but occurs in up to 14% of all patients following a procedure and up to 50% in patients with pre-existing chronic kidney disease (CKD),¹ making AKI one of the most prevalent adverse events.^{2,3,7} Reducing the prevalence AKI is a patient safety objective set forth by the National Quality Forum.¹⁶ When AKI occurs, patients have an increased risk of

[figure not shown]
PROTOCOL

(Version #: 6, version date: 9-21-20)

cardiovascular events, prolonged hospitalization, end-stage renal disease, all-cause mortality, and increased acute care costs of over \$7,500 per case.^{8,11,17} Based on our preliminary evidence in our pilot demonstrating a statistically significant 28% reduction in AKI in patients with pre-existing CKD, we estimate that over 70,000 AKI events could be prevented with an annual cost savings of \$525 million each year nationally using evidence based strategies delivered through a Virtual Learning Collaborative (VLC) in common diagnostic procedures using contrast dye.

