2020

IMPROVE AKI Cluster- Randomized Trial (IMPROVE-AKI)

NCT03556293

09-21-2020

Statistical Analysis

We estimated the effect of both the implementation strategy and information support interventions, as well as their interaction, using hierarchical logistic regression models for 7-day postprocedural AKI. Models were fit using patient-level data with and without adjustment for the 20 patient-level characteristics in the VA-derived AKI risk prediction model underlying the Surveillance dashboard.²³ To account for site-level variation, observations were clustered at the site level, and models included a site-level random effect and controlled for site baseline risk-adjusted performance (observed to expected outcome ratio) in the 12 months before the study period. The decision to adjust for site baseline risk adjusted performance and other patient characteristics was prespecified. We implemented Satterthwaite small-sample correction because of the small number of clusters. Interim analyses and stopping criteria were not performed when determining sample size. In all models, the key features of interest were the interaction between implementation strategy and information support interventions, as well as differences across the four intervention combinations, with Assistance specified as the reference intervention. We estimated odds ratios (ORs) and 95% confidence intervals for pairwise comparisons of each combination of interventions and applied the Bonferroni correction for multiple comparisons. Analyses were run for the entire population and separately within the CKD subset. Corresponding sensitivity analyses modeled 30-day postprocedural AKI. Analyses were conducted using R 4.1.2.²⁶

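### The cost-effectiveness plan compares each strategy only with TA, so it does not give the cost per AKI prevented of adding ASR to VLC

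*Protocol*

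**What the plan says.** The paragraph on cost-effectiveness in Protocol C.7 opens with its purpose: "We will assess both the clinical effectiveness in AKI reduction and the two interventions' cost-effectiveness". The method is then "estimating the incremental cost for each incremental AKI prevented above the TA only baseline and stratified across the other three clusters". The word for stratification is loose, but the plain reading is three ratios, one each for TA+ASR, VLC and VLC+ASR, all with TA as comparator. The same paragraph adds that a "separate budget impact analysis for implementing the VLC arm and stratified by ASR will be generated", which concerns cost and has no effect in a denominator. It gives no ordering by cost, no dominance rule, no threshold and no method for uncertainty. The SAP does not mention cost-effectiveness.

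The clinical plan is wider. The Objective asks whether "VLC coaching augmented by ASR (VLC+ASR) will lead to better patient outcomes compared to TA, TA + ASR, and VLC alone", and C.1 repeats this as the working hypothesis. C.11 powers all six pairwise differences between strategies. The SAP reports them: "We estimated odds ratios (ORs) and 95% confidence intervals for pairwise comparisons of each combination of interventions".

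**The concern.** A hospital system can run only one of the four strategies. For such a choice, the relevant price of a costlier strategy is its extra cost per extra AKI prevented over the next less costly strategy still worth considering. A ratio against a common baseline averages the productive and unproductive parts of a package. If VLC does all the work, VLC+ASR still inherits VLC's effect when it is compared with TA, and the ratio can look favourable although the money spent on ASR bought nothing.

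The TA+ASR versus TA ratio cannot stand in for the missing contrast. Specific Aim 1 expects ASR to have a larger effect alongside VLC than alongside TA, so an ASR result under TA need not carry over. What is at stake is the economic answer on ASR as an addition to VLC, which the stated purpose of the evaluation covers.

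**Working it through.** **Inputs from the documents.** C.11 states: "proportion of AKI in the VLC and VLC+ASR arms are assumed to be 0.2700 under the null hypothesis and 0.2025 under the alternative" hypothesis; TA and TA+ASR are both projected at 0.2700. It also gives 661 patients per hospital, 4 hospitals and 2,644 patients per arm, and an intra-cluster correlation of 0.0009. Section A gives "increased acute care costs of over" $7,500 per AKI case.

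**Assumed inputs.** The documents give no strategy costs. The main illustration assumes $60,000 per hospital for VLC and $60,000 for ASR, both over TA. The wider range is $25,000 to $100,000 for VLC and $10,000 to $100,000 for ASR.

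**1. Check that the C.11 inputs are read as the plan reads them.** There is no stated cost-effectiveness figure to reproduce, so the power figures resting on the same rates were checked.
- Design effect = 1 + (661 − 1) × 0.0009 = 1.594.
- Effective n per arm = 2,644 / 1.594 = 1,659.
- Two-sided normal approximation for 0.2700 versus 0.2025: power 99.6% at 0.05 (stated: above 99%) and 97.4% at 0.05/6 (stated: above 97%).

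Both figures reproduce.

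**2. AKI prevented against TA.** 661 × (0.2700 − 0.2025) = 661 × 0.0675 = 44.6 per hospital, for VLC and for VLC+ASR alike. Per arm: 2,644 × 0.0675 = 178.5.

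**3. Ratios per hospital, $60,000 each for VLC and ASR (assumed).**

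| Contrast | Extra cost | AKI prevented | Cost per AKI prevented |
|---|---|---|---|
| VLC vs TA (planned) | $60,000 | 44.6 | $1,345 |
| VLC+ASR vs TA (planned) | $120,000 | 44.6 | $2,690 |
| TA+ASR vs TA (planned) | $60,000 | 0 | none: TA dominates |
| VLC+ASR vs VLC (not planned) | $60,000 | 0 | none: VLC dominates |

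**4. Dependence on the assumed costs.** Over the wider range, VLC+ASR versus TA runs from 4 × $35,000 / 178.47 = $784 to 4 × $200,000 / 178.47 = $4,483. It stays below $7,500 up to a combined extra cost of 7,500 × 178.47 = $1,338,525 per arm, or about $335,000 per hospital, with no ASR effect at all. Against VLC the denominator is 0 throughout, so the dominance needs only a positive ASR cost.

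**5. A small real ASR effect.** Suppose ASR lowers risk by a further 0.25 percentage points and VLC and ASR each cost an assumed $50,000 per hospital ($200,000 per arm).
- Extra AKI prevented per arm: 2,644 × 0.0025 = 6.61.
- Against TA: $400,000 / (178.47 + 6.61) = $2,161 per AKI prevented.
- Against VLC: $200,000 / 6.61 = $30,257 per AKI prevented.

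The planned ratio hardly registers how dear the last step is.

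**6. Precision of the missing contrast.** With both VLC arms at 0.2025, the standard error of the difference is √(2 × 0.2025 × 0.7975 / 1,659) = 0.0140, or about 37 AKI per arm. The 95% half-width is 1.96 × 0.01395 = 0.0273, about 72 AKI per arm. If ASR truly adds nothing, chance alone would put VLC+ASR ahead in about half of such trials. The direct contrast therefore needs its own interval.

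**The case against.** The strongest reply is that little is hidden. In the table above, VLC and VLC+ASR prevent the same number of AKI and one ratio is twice the other, so the dominance is visible to anyone who reads both rows. All three planned ratios share a baseline, so any other contrast follows by subtraction once arm-level costs and AKI counts are reported. In this scenario TA+ASR versus TA also shows ASR buying nothing. The budget impact analysis splits VLC by ASR, and the AKI analysis compares VLC+ASR with VLC, so both halves of the missing ratio are partly in hand.

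Much of this stands. A reader might infer that dominance cannot be seen under the plan; it can, if costs and counts by arm are published, but the plan does not promise that. The agreement between the TA and VLC layers holds only because this planning alternative has no interaction. In the interaction scenario that C.11 also considers (only VLC+ASR at 0.2025, the other arms at 0.2700), TA+ASR versus TA prevents 0 AKI while VLC+ASR versus VLC prevents 178.5 per arm. And deriving a ratio afterwards from two point estimates gives it no pre-specified comparator and no interval.

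It is also fair to say that zero ASR benefit is a power-planning input. The working hypothesis is that VLC+ASR is better than VLC alone.

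**Conclusion.** The concern holds in a limited form. The economic plan leaves out a contrast that the trial asks about clinically, and ratios against TA do not supply it. At the protocol's own planning rates, VLC+ASR could show about $2,690 per AKI prevented against TA while costing more than VLC for no further benefit. The dollar figure rests on assumed costs; the dominance rests only on the C.11 rates and a positive ASR cost. The cost order of TA+ASR and VLC is not given, so the right comparator for each strategy has to come from observed costs.

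Three stronger readings are tempting and unsupported:
- That the plan contains a rule that would recommend VLC+ASR. It states no threshold or decision rule, and the $7,500 is a background figure for acute care cost, used here only as a yardstick.
- That the dissemination choice in C.22 rests on these ratios. That section refers to the evaluation of the interventions as a whole and does not mention the economic analysis.
- That the SAP's odds ratios would serve as the economic denominator. No document says so; C.7 asks for AKI prevented, an absolute quantity that the planned model can provide.

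The primary AKI analysis, the design and the data collection are unaffected.

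**What to change.** Revise the cost-effectiveness paragraph in C.7 as follows.

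- Rank the four strategies by observed cost and remove those that are dominated or extendedly dominated. Report each remaining strategy's incremental cost per AKI prevented against the next less costly non-dominated one. Net benefit for all four strategies over a range of values per AKI avoided is an acceptable alternative.
- Report VLC+ASR versus VLC in any case, as extra cost and extra AKI prevented, stating dominance where there is no gain.
- Take AKI prevented from absolute risk differences by arm, standardized from the planned hierarchical logistic model.
- Give uncertainty by a method that respects hospital clustering, such as resampling hospitals within arm, with a caution that there are as few as 4 per arm.
- Keep the ratios against TA as a supplement if wanted.

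The cost is one reworded paragraph and a small amount of extra analysis on the same data.

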We will be using the COVID Shared data resource to identify overall rates of testing and COVID positivity at each site that has a cath lab to get a sense of COVID impact at that site. We will also be linking each of the cath patients to COVID testing status to get a sense of how often they were tested, and how many were cath'ed and COVID+. Lastly, we will assess whether COVID+ status had enough patients amonth cath patients to warrant inclusion as a risk factor, since AKI is a risk factor from covid. We will not be

Table 1. VA Site Characteristics		
Site	Region	Procedure Volume
554	1	1131
691	1	807
605	1	545
654	1	292
580	2	1794
549	2	1605
671	2	1015
537	2	629
586	2	341
626	3	1621
637	3	692
672	3	632
544	3	335
528*	4	1617
512	4	326
693	4	266
632	4	49

*2 sites

PROTOCOL

(Version #: 6, version date: 9-21-20)

analyzing any case level data from non-cath patients, but will use the COVID shared resource to aggregate as above.

C.3. AKI Prevention Toolkit. *Intervention:* All sites will receive the AKI Prevention Toolkit (**Appendix 1**) including 3 core interventions: 1. Standardized order sets; 2. IV and oral fluids; and 3. Reduced contrast volume. The interventions adhere to the KDIGO guidelines¹³ and add interventions developed and tested in our pilot intervention to implement AKI preventive strategies.^{1,3} We will also educate the sites on the hemodynamic guided fluid administration for volume expansion guidelines and PRESERVE results when released.^{57,58}

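### C.11's interaction power of just above 90% and pairwise power above 97% fit only equal-sized hospitals and large-sample critical values; unequal sizes and the SAP's small-sample correction each lower them

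*Protocol*

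**What the plan says.** Protocol C.11 states: "The target enrollment of approximately 2,644 is planned in each of the four arms of the study", "with four hospitals within each arm (average approximately 661 patients per hospital". The AKI proportion in the VLC arms is "0.2700 under the null hypothesis and 0.2025 under the alternative hypothesis (an effect size of 25% or 0.0675"; the TA arms are projected at 0.27. The intra-cluster correlation is put at a value "of 0.0009 – this is implied by the intervention arm of the pilot study". Tests are at the 0.05 level and the power target is at least 90%.

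From these inputs C.11 reports that "the power to detect a significant interaction between TA/VLC and ASR status is just above 90" per cent and that "testing the full set of 6 pairwise differences among the four intervention strategies has power >97" per cent after Bonferroni correction. It mentions a penalty for clustering but prints no formula, and it gives no measure of how hospital size varies.

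Three other places bear on this:
- The table headed "Table 1. VA Site Characteristics" lists procedure volumes from 49 to 1,794 in 17 rows, one of which covers two sites. C.2.b describes these as sites that initially met the criteria, and C.14 says that the two excess lowest-volume sites will be excluded.
- The SAP says: "We implemented Satterthwaite small-sample correction because of the small number of clusters".
- C.18 carries the Aim 1 power over to Aim 2 unchanged.

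**The concern.** An average cluster size is enough for a design effect only when clusters are about equal. When they are not, the effective sample size is smaller. Likewise, a normal or large-df critical value is too lenient when arms are compared across 16 hospitals, and the SAP's own analysis recognises this. C.11 shows no sign of allowing for either.

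The interaction is where it matters. Aim 1 hypothesises that ASR has a bigger impact with VLC than with TA. C.7 uses the significance of the interaction to decide whether separate effects or pooled main effects are reported, and the SAP names the interaction as a key feature. C.11 claims to meet its 90% floor for this test, with almost no margin. C.12 then describes the power calculation as probably too conservative. If the true power is lower, a real interaction is more likely to be missed and the term dropped.

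**Working it through.** **Inputs from C.11.** n = 2,644 per arm, mean cluster size m = 661, ICC = 0.0009, difference 0.0675, interaction cells 0.27, 0.27, 0.27 and 0.2025. Tests are taken as two-sided, since C.11 does not say.

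**1. Reproducing the stated figures (equal hospitals, normal test).**
- Design effect DE = 1 + (661 − 1) × 0.0009 = 1.594.
- Interaction variance, two-rate form: V = 2 × (0.27 × 0.73 + 0.2025 × 0.7975) = 0.7172. SE = √(0.7172 × 1.594 / 2,644) = 0.0208. 0.0675/SE = 3.246, and Φ(3.246 − 1.960) = **90.1%**.
- With cell-specific variances, V = 3 × 0.1971 + 0.1615 = 0.7528 and power is 88.7%. On the logit scale it is 91.2%. With no clustering penalty (cell-specific variances) it would be 97.9%, so a penalty was evidently applied.
- One pair at 0.05/6: V = 0.3586, SE = 0.0147, 0.0675/SE = 4.591, and Φ(4.591 − 2.638) = **97.5%**.

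Both stated figures are matched.

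**2. Unequal hospital size.** Assume that CKD counts vary as Table 1 volumes do. Splitting the two-site row evenly (1,617/2 = 808.5 each) gives 18 sites. Dropping the two smallest (49 and 266) leaves 16, ranging from 292 to 1,794, with total 13,382, mean 836.4, SD 467.0 and CV = 467.0/836.4 = 0.558.
- CV-inflated: DE = 1 + ((0.558² + 1) × 661 − 1) × 0.0009 = 1.779.
- Efficient weighting, as a hospital random-effect model would give: scale volumes to w with mean 661; DE = 661 / mean[w/(1 + (w − 1) × 0.0009)] = 1.709.

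**3. Small-sample degrees of freedom.** Assume 16 hospitals − 4 cell means = 12 df. The critical value rises from 1.960 to 2.179 for the interaction, and from 2.638 to 3.153 for a Bonferroni pair. Power comes from the noncentral t distribution.

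**4. Results (%).** Interaction entries are two-rate form (cell-specific; logit).

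| Case | DE | Interaction, normal | Interaction, 12 df | One pair, normal | One pair, 12 df |
|---|---|---|---|---|---|
| Equal, 661 | 1.594 | 90.1 (88.7; 91.2) | 84.6 (82.8; 85.9) | 97.5 | 90 |
| 16 sites, CV-inflated | 1.779 | 86.7 (85.1; 88.0) | 80.5 (78.6; 82.0) | 95.6 | 86 |
| 16 sites, weighted | 1.709 | 88.0 (86.4; 89.2) | 82.0 (80.2; 83.5) | 96.4 | 87 |

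With all 17 rows as listed (CV 0.675, DE 1.865) the interaction is 85.1 (83.4; 86.4), or 78.7 (76.7; 80.2) with 12 df. Over the site lists, the three variance forms and both weightings, the range is about 83-89% with normal critical values and 77-84% with 12 df.

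**5. How little variation is needed.** In the form that gives 90.1%, CV = 0.10 gives DE = 1 + (1.01 × 661 − 1) × 0.0009 = 1.600 and power just under 90%. On the logit scale the ratio of effect to SE is 3.31 at DE 1.594 and must stay above 1.960 + 1.282 = 3.242. That allows DE up to 1.594 × (3.31/3.242)² = 1.662, so CV² = (1.662 − 1.594)/(661 × 0.0009) = 0.114 and CV is about 0.34, still well below 0.56.

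**The case against.** The strongest defence is that Table 1 does not give the trial's cluster sizes. It counts procedures with no stated period, whereas C.11's assumptions are for CKD patients. It lists candidate sites, and C.14 speaks of 29 recruited and a minimum of 16 enrolled. The CV of the enrolled sites is therefore unknown. This stands, and it is why the result is a range. It does not restore the stated figure, because CKD counts would have to be far more uniform than the volumes are.

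A second defence is that the CV-inflated design effect weights every patient equally, while the planned hierarchical model down-weights large hospitals. This also stands. With efficient weighting, unequal size costs about 2 points (90.1% to 88.0%) instead of 3.4.

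A third is that C.11 takes no credit for adjustment for patient risk, nor the SAP's power for site baseline performance, and either could offset a small loss. The documents do not quantify this, so it cannot be relied on or ruled out.

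A reader might infer three stronger things, and the documents support none of them:
- That the trial hospitals range from 49 to 1,794. C.14's exclusion would remove the smallest site if Table 1 is the list.
- That interaction power is 85%, a 5-point loss from unequal size. That value belongs to the cell-specific variance form, whose equal-size baseline is 88.7%.
- That unequal size takes power to about 79%. Degrees of freedom alone take 90.1% to 84.6% with equal hospitals, which is the larger of the two effects. The SAP also states no df, so 12 is an assumption.

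**Conclusion.** The point holds as a statement about C.11's figures. They match equal hospitals and normal critical values, and C.11 relies on them to say that its 90% floor is met for the interaction.

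At the stated ICC of 0.0009, unequal size brings the interaction to about 85-88% and one Bonferroni pair to about 96% on the 16-site list. The df correction alone brings them to about 83-85% and 90%. Both together bring them to about 77-84% (all site lists) and 86-87% (16-site list).

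This rests on four assumptions: the design-effect formula, inferred because it reproduces both stated figures; Table 1 variation standing in for CKD counts; 12 site-level df; and two-sided tests.

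A reader might conclude that the design is broadly underpowered or needs more patients. The calculation does not show that. The claim of above 99% for VLC within a level of ASR survives unequal size with normal critical values (99.6% falls to 99.2% at DE 1.779).

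**What to change.** Recalculate C.11 using the cluster-size CV of CKD patients at the enrolled hospitals, with the CV-inflated design effect or the mixed-model weighted equivalent, and t critical values with the site-level df that the SAP's correction implies. State the formula, the CV, the df and the sidedness. Show the unequal-size effect and the df effect separately, then combined.

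Replace the figures of just above 90% and above 97% with the resulting ranges, and withdraw the statement that interaction power is above 90%. Revisit C.12's remark that the calculation is probably too conservative. Repeat the change in C.18, which reuses these powers for Aim 2.

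The cost is a recalculation and revised wording. The stated power becomes less favourable, and no extra patients are needed.
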